## **6.4. ONCT-534**

### **6.4.1. Description of ONCT-534**

ONCT-534 is a DAARI with a novel mechanism of action that includes inhibition of AR function and degradation of the AR protein mediated by interaction with the NTD of the AR. ONCT-534 has demonstrated preclinical activity in prostate cancer models against both unmutated AR, and against multiple forms of AR alteration, including those with AR amplification, mutations in the AR LBD, and splice variants with loss of the AR LBD.

ONCT-534 is manufactured as a bulk drug substance and formulated into drug product tablets at strengths of 40 mg and 200 mg as scored (bisectable), white to off-white non-coated tablets, providing doses of 20 mg and 100 mg respectively when separated into 2 halves along the scoring.

#### **6.4.2. Handling and Accountability of ONCT-534**

Further information regarding ONCT-534 handling and accountability can be obtained from the Pharmacy Manual and the current Investigator's Brochure for ONCT-534.

#### **6.4.3. Packaging and Labeling of ONCT-534**

ONCT-534 will be provided as scored (bisectable) 40 mg and 200 mg tablets. The tablets will be packaged in 30 cc round white bottles, which will be closed with an induction seal and child-resistant plastic screw caps. The 40 mg bottles will contain 30 tablets and the 200 mg bottles will contain 20 tablets. Country-specific labels will be applied to adhere to local regulations regarding labeling requirements.

#### **6.4.4. Shipping, Storage, and Stability of ONCT-534**

Bottles of ONCT-534 should be shipped and stored at a controlled room temperature of 20°C to 25°C with excursions permitted to 15°C to 30°C. Shipments of ONCT-534 will be temperature monitored while in transit. ONCT-534 should be stored in an access controlled and temperature monitored storage location until the time of dispensation. It is recommended that the tablets be retained in the original package until used.

Subjects should store ONCT-534 in a secure location at room temperature and protect it from extreme heat or cold.

## **7. STUDY DISCONTINUATION AND PARTICIPANT DISCONTINUATION/WITHDRAWAL**

### **7.1. Reasons for Subject Removal from the Study**

Reasons for subject discontinuation from the study may include the following:

- Progressive disease and no longer clinically benefiting from treatment.
- Development of unacceptable toxicity.
- Withdrawal of consent.
- Loss to follow-up.
- Study termination by the Sponsor.
- Death.

PCWG3 ([Scher et al., 2016](#)) introduces the concept of no longer clinically benefiting to underscore the distinction between first evidence of progression and the clinical need to

terminate or change treatment, and the importance of documenting progression in existing lesions as distinct from the development of new lesions.

Treatment beyond preliminary evidence of progression (e.g., unconfirmed progressive disease according to PCWG3) or radiologic progression for measurable disease according to RECIST v1.1 is permitted for subjects who may derive benefit from continued study participation (in the opinion of the Investigator and in consultation with the Sponsor), provided the subject is clinically stable, and is able to continue treatment until the next imaging assessment. One example of preliminary evidence of progression is the appearance of new abnormalities on the first bone scan after starting ONCT-534 treatment.

To continue treatment beyond preliminary evidence of progression, the following criteria must be met:

- Absence of signs and symptoms indicating clinically significant progression of disease.
- No decline in ECOG or Karnofsky performance status ([Appendix 1](#)).
- Absence of symptomatic rapid disease progression requiring urgent medical intervention (e.g., symptomatic pleural effusion, spinal cord compression).
- Reconsent using a written informed consent document that details all Regulatory Authority-approved therapy, and potential clinical benefit, that the subject may be foregoing to continue receiving the investigational product.

An End of Treatment visit should be conducted for subjects who discontinue prior to the Week 108 visit as indicated in the Schedule of Assessments (see Section 1.3). Subjects will be contacted for a safety assessment 30 days (+7 days) after the last dose of ONCT-534 for all subjects who discontinue treatment (either at Week 108 or Early Termination).

Every effort should be made to obtain a reason for subject discontinuation from the study, and to obtain the assessments listed. The reason for study discontinuation should be documented in the eCRF. If a subject withdraws from the study, study staff may search hospital or public records to obtain survival information.

Subjects with global deterioration of health status requiring discontinuation of treatment without objective evidence of disease progression at that time should be classified as having symptomatic deterioration. Every effort should be made to document the objective progression, even after discontinuation of treatment.

For subjects who discontinue from the study, the date and type of next systemic therapy for mCRPC should be collected.

## 7.2. Subject Replacement

The BOIN design does not require that subjects in the Phase 1 portion of the study who are not DLT evaluable (as defined in Section 9.2) be replaced unless the cohort size is one. Subjects who receive ONCT-534 and withdraw prior to Day 28 due to a DLT will not be replaced, and subjects who are not evaluable may be replaced at the discretion of the Sponsor and SRC.

Subjects in the Phase 2 portion of the study may be replaced, after discussing with the Sponsor, if they are not evaluable for efficacy (as defined in Section 9.2) for the purpose of estimating clinical activity of ONCT-534 and discontinued the study for reasons not related to study drug or disease progression.

Additional subjects may be enrolled beyond the planned sample size to provide sufficient data for analysis of safety, efficacy, PK and/or pharmacodynamics.

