## **9.2. Populations for Analysis**

The DLT-evaluable Population is defined as all subjects in the Phase 1 Dose Escalation part of the study who receive ONCT-534 and either complete the 28-day DLT observation period or discontinue the study early due to a DLT. Subjects will be grouped by the dose received.

The Safety Population is defined as all subjects who receive at least one dose of ONCT-534. Subjects will be grouped by the ONCT-534 dose received at study entry.

The Efficacy-evaluable Population is defined as all subjects who receive ONCT-534 and complete at least one post-treatment disease assessment and do not discontinue due to clinical evidence of disease progression without documentation prior to obtaining post-treatment disease assessment. Subjects will be grouped by dose received.

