## 9.5. Analysis of Endpoints

### 9.5.1. BOIN Design Implementation and Assessment of MTD

A BOIN design will be employed to find the MTD. The BOIN design is implemented in a simple way incorporating features of the traditional 3+3 design but is more flexible and possesses superior operating characteristics that are comparable to those of more complex model-based designs, such as the continual reassessment method (Zhou et al., 2018). Operating characteristics will be detailed in the SAP.

[figure not shown]
The target DLT rate for the MTD is  $\phi = 0.3$  and the maximum sample size is 27, using an accelerated titration design for the first 2 dose levels. DLTs are defined in Section 8.3.7, and those DLTs that occur within the first 28 days of treatment will be used for dose finding. As shown in

Figure 1, the BOIN design uses the following rule once it has moved from a cohort size of 1 to 3, optimized to minimize the probability of incorrect dose assignment, to guide dose escalation/de-escalation:

- If the observed DLT rate at the current dose is  $\leq 0.236$ , escalate the dose to the next higher dose level;

- If the observed DLT rate at the current dose is  $> 0.359$ , de-escalate the dose to the next lower dose level;
- If the above criteria are not met, remain at the current dose until a maximum of 12 subjects have been enrolled and treated at that dose level.

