**Figure 1: Flowchart for Trial Conduct Using the BOIN Design**

\* DLT rate =  $\frac{\text{Total number of patients who experienced DLT at the current dose}}{\text{Total number of evaluable patients treated at the current dose}}$

For the purpose of overdose control, doses  $j$  and higher levels will be eliminated from further consideration if  $\Pr(p_j > 0.3 \mid \text{data}) > 0.95$  and at least 3 evaluable subjects have been treated at dose level  $j$ , where  $p_j$  is the true DLT rate of dose level  $j$ ,  $j = 1, \dots, 5$ . This posterior probability is evaluated based on the beta-binomial model  $y_j \mid p_j \sim \text{binomial}(p_j)$  with  $p_j \sim \text{uniform}(0, 1)$ , where  $y_j$  is the number of subjects that experience DLT at dose level  $j$ . If the lowest dose is eliminated, the SRC will decide whether to stop the study or add a lower dose level. The

probability cutoff 0.95 is chosen to be consistent with the common practice that when the target DLT rate  $\phi \leq 1/6$ , a dose with 2/3 subjects experiencing DLT is eliminated.

The above dose escalation/de-escalation/elimination rule, which will be used to conduct the trial, is equivalently shown in

Table 5.

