**Table 5: Dose Escalation/De-escalation/Elimination Rule for the BOIN Design**

Actions*	The number of evaluable subjects at the current dose (cohort size n=3)											
	1	2	3	4	5	6	7	8	9	10	11	12
Escalate if # of DLT $\leq$	0	0	0	0	1	1	1	1	2	2	2	2
De-escalate if # of DLT $\geq$	1	1	2	2	2	3	3	3	4	4	4	5
Eliminate if # of DLT $\geq$	NA	NA	3	3	4	4	5	5	5	6	6	7

The steps to implement the BOIN design are described as follows:

1. All decisions to move from one dose level to another will be made by the SRC (Section 10.1.4), guided by the principles of the BOIN design.
2. Perform accelerated titration in dose cohorts 1 and 2 as follows. Treat the first subject in the cohort and escalate the dose in a one-subject-per-dose-level fashion until any of the following events is observed in the first 28 days of treatment: (i) a DLT, (ii) an existing Grade 2 condition that worsens to Grade 3; or (iii) a new Grade 2 AE. In such a case, the cohort size for the current and all subsequent cohorts will be increased to 3.
3. To assign a dose to the next cohort of subjects, the SRC will consider dose escalation/de-escalation rules presented in

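### Once Phase 1 cohorts are of size 3, no minimum number of DLT-evaluable subjects is stated for escalation, so Table 5 permits it on 0/1 or 0/2

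*Combined protocol and SAP*

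**What the plan says.** - **Replacement (Section 7.2).** "The BOIN design does not require that subjects in the Phase 1 portion of the study who are not DLT evaluable" be replaced, with an exception for cohorts of one. In any other cohort, "subjects who are not evaluable may be replaced at the discretion of the Sponsor and SRC".
- **Who counts (Section 9.2).** A DLT-evaluable subject has received ONCT-534 and must "either complete the 28-day DLT observation period or discontinue the study early due to a DLT". The DLT rate under Figure 1 in Section 9.5.1 uses evaluable subjects as its denominator.
- **Cohort size (Sections 9.1.1 and 9.5.1).** The "maximum sample size is 27, using an accelerated titration design for the first 2 dose levels". Single-subject cohorts are confined to those two levels. On a DLT or a Grade 2 trigger there, "In such a case, the cohort size for the current and all subsequent cohorts will be increased to 3".
- **Decision table (Section 9.5.1, Table 5).** The columns are headed "The number of evaluable subjects at the current dose (cohort size n=3") and run from 1 to 12. At 1 and at 2 evaluable subjects the entries are: escalate at 0 DLTs, de-escalate at 1 or more, eliminate not applicable.
- **Elimination (Section 9.5.1).** A dose is eliminated only if "at least 3 evaluable subjects have been treated at dose level" and the posterior criterion is met.
- **Authority (Section 9.5.1, step 1).** The SRC makes every decision to change dose level, guided by the BOIN principles.

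**The concern.** Read together, these provisions leave a gap. The plan moves to cohorts of 3 for the higher doses of a drug not previously given to humans. But if one or two of the three subjects leave before Day 28 for reasons other than a DLT, nothing visible requires the cohort to be filled before Table 5 is read. With two of three lost at 300 mg and no DLT in the third, the table reads escalate to 600 mg on 0/1.

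The protection is also uneven. At 40 and 80 mg, while the cohort size is one, a non-evaluable subject has to be replaced, and a new Grade 2 AE or a worsening from Grade 2 to Grade 3 stops single-subject escalation. In a depleted cohort of 3 at a higher dose, replacement is optional and Table 5 counts only DLTs. A subject who stops early for toxicity short of a DLT is not evaluable under Section 9.2 and drops out of the denominator.

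At stake is how much evidence stands behind a step up to a higher dose.

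**Working it through.** **1. Reproduce the plan's boundaries and Table 5.** The target is φ = 0.3 (Section 9.5.1). The documents do not give the two BOIN interval parameters; I assumed φ1 = 0.6φ = 0.18 and φ2 = 1.4φ = 0.42.

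- Escalation boundary: ln[(1−φ1)/(1−φ)] / ln[φ(1−φ1)/(φ1(1−φ))] = ln(0.82/0.70) / ln(0.246/0.126) = 0.2365 (plan: 0.236).
- De-escalation boundary: ln[(1−φ)/(1−φ2)] / ln[φ2(1−φ)/(φ(1−φ2))] = ln(0.70/0.58) / ln(0.294/0.174) = 0.3585 (plan: 0.359).

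Applying the plan's boundaries, and its uniform-prior elimination criterion for n ≥ 3, reproduces all three rows of Table 5 for every n from 1 to 12. The table is computed correctly, and 0/1 and 0/2 do read 'escalate'.

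**2. Evidence behind each reading.** Under the plan's uniform prior, Pr(p > 0.3 | 0 DLTs in n) = 0.7^(n+1): 0.490 for n = 1, 0.343 for n = 2, 0.240 for n = 3.

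**3. Chance of an 'escalate' reading for a given number evaluable.** At 1, 2 or 3 evaluable subjects, escalation requires 0 DLTs, so the chance is (1−p)^n.

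| True DLT rate p | n = 1 | n = 2 | n = 3 |
|---|---|---|---|
| 0.3 | 0.700 | 0.490 | 0.343 |
| 0.4 | 0.600 | 0.360 | 0.216 |
| 0.5 | 0.500 | 0.250 | 0.125 |

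**4. How often a cohort of 3 is depleted.** Let d be the probability that a subject is non-evaluable for a non-DLT reason. The documents give no value, so d = 0.1 and 0.2 are assumptions. With no replacement, the number evaluable is binomial(3, 1−d).

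| Number evaluable | Formula | d = 0.1 | d = 0.2 |
|---|---|---|---|
| 3 | (1−d)³ | 0.729 | 0.512 |
| 2 | 3(1−d)²d | 0.243 | 0.384 |
| 1 | 3(1−d)d² | 0.027 | 0.096 |
| 0 | d³ | 0.001 | 0.008 |

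Two evaluable subjects is much the likelier shortfall. Zero evaluable has no column in Table 5 and gives no escalation.

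**5. Weighted chance of an 'escalate' reading from the first cohort at a dose.** This is the sum over n = 1, 2, 3 of P(n evaluable) × (1−p)^n.

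- p = 0.4, d = 0.1: 0.027×0.600 + 0.243×0.360 + 0.729×0.216 = 0.261
- p = 0.4, d = 0.2: 0.096×0.600 + 0.384×0.360 + 0.512×0.216 = 0.306
- p = 0.5, d = 0.1: 0.027×0.500 + 0.243×0.250 + 0.729×0.125 = 0.165
- p = 0.5, d = 0.2: 0.096×0.500 + 0.384×0.250 + 0.512×0.125 = 0.208

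Against a full cohort (0.216 and 0.125), the rise is 4.5 to 9.0 percentage points at p = 0.4 and 4.0 to 8.3 points at p = 0.5.

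**The case against.** **The SRC decides, and Table 5 only guides.** Every dose move is an SRC decision based on all available data, and the Sponsor and SRC may replace a non-evaluable subject in any cohort. This stands, and it rules out the reading that the protocol forces escalation on one subject or cancels the three-subject cohort. It does not supply a floor: the rule the committee is guided by still reads 'escalate'.

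**The replacement policy looks deliberate, and BOIN can be run with unequal cohorts.** Also true, and Table 5 contains no calculation error. The point is only that no minimum is stated for escalation.

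**Different minimums for elimination and escalation can be defended.** Elimination removes a dose and all higher ones from consideration, whereas escalation can be followed by de-escalation. Columns 1 and 2 also de-escalate on a single DLT, and subjects who discontinue because of a DLT stay in the denominator. The asymmetry alone is therefore not an error.

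**A reader might infer that the n = 1 column contradicts accelerated titration**, because 1/1 reads 'de-escalate' while step 2 enlarges the current cohort to 3. The documents do not support this. Section 9.5.1 applies the interval rule only after the cohort size has moved from 1 to 3, Table 5 is headed for cohorts of 3, and step 2 gives a single action for a DLT in a titration subject. Expansion comes first and the table is read afterwards.

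**The text reviewed is incomplete.** The implementation steps break off within step 3, the asterisk in the Table 5 header has no visible note, and the Figure 1 flowchart is not shown. A minimum could sit in any of these, which limits confidence.

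**Conclusion.** The point holds as a gap in the written rule. Once the cohort size is 3, the visible text permits escalation on 0/1 or 0/2 evaluable subjects, and the only three-evaluable minimum it states is for elimination. This is worth correcting before the higher dose levels open, but it is neither an automatic escalation nor a conflict between instructions.

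The size is moderate. At true DLT rates of 0.4 and 0.5, the chance of an 'escalate' reading from the first cohort rises by about 4 to 9 percentage points. That rests on an assumed 10% to 20% non-evaluable rate, loss that is independent of DLT risk, no replacement, and the SRC following the table. At those loss rates and under independence, the figures are a ceiling, because any replacement or SRC caution lowers them. The contrast of 60% on one subject with 21.6% on three at a rate of 0.4 is correct as a conditional comparison, but it overstates the effect unless weighted by how rarely only one subject remains.

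**What to change.** - In Sections 7.2 and 9.5.1, state that outside accelerated titration an escalation decision needs the full planned cohort of 3 DLT-evaluable subjects at the current dose, with non-evaluable subjects replaced to reach it. This reconciles the replacement text with the plan's own cohort size.
- In Table 5, mark the 'Escalate' entries in columns 1 and 2 as not applicable outside accelerated titration.
- If a minimum already appears after step 3, in the Table 5 note or in Figure 1, cross-refer to it in Section 7.2 instead.

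The cost is a few sentences, an occasional replacement subject, and up to about one more 28-day DLT window when a cohort loses a subject. Replacement is already permitted, and Section 4.1.1 counts the approximately 27 Phase 1 subjects as evaluable subjects, so the planned number of evaluable subjects need not change.

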### Study Procedures

At specific timepoints as outlined in the Schedule of Assessments (Table 1), subjects will undergo assessments/procedures including providing informed consent, interviews, and testing to determine eligibility, disease assessments by computed tomography scan and bone scan,

electrocardiogram, blood tests for hematology, clinical chemistry, PSA levels, ONCT-534 PK, and biomarkers.

Throughout the conduct of the study, subjects will be asked to report concomitant medications and AEs and will have their disease reassessed.

[figure not shown]

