#### **8.1.1.4. Eligibility Testing**

Results of the following must be available to determine eligibility:

- Clinical chemistry (see Section [8.1.5](#)).
- Clinical hematology and coagulation (see Section [8.1.7](#)).
- Physical examination (see Section [8.1.2](#)).
- Disease assessment to verify measurable or evaluable disease (see Section [8.2](#)).
- ECOG performance status (see [Appendix 1](#)).
- PSA level (see Section [8.1.6](#)).
- 12 lead ECG (see Section [8.1.4](#)).
- Serum testosterone level in the local laboratory.

Test results obtained within 28 days of the planned first day of ONCT-534 administration may be used.

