### **9.1.2. Phase 2 Dose Expansion**

In the Phase 2 portion of the study, up to 16 evaluable subjects will be randomized into each of 2 expansion dose cohorts and evaluated for efficacy using a Simon 2-stage minimax design to exclude a response rate of < 10%, where response is defined as having  $\geq 50\%$  reduction in PSA. The hypothesized response rate under treatment is  $\geq 40\%$  and will be evaluated using a one-sided type I error rate of 0.025 with 80% power. A total of 9 subjects per dose level will be randomly assigned in Stage 1. If at least 2 responses of  $\geq 50\%$  reduction in PSA are observed, the dose level will proceed to Stage 2. If at least 5 responses are observed in a total of 16 subjects per dose level, the null hypothesis will be rejected.

Randomized dose assignment will proceed when both cohorts are open for enrollment. If one of the dose levels is closed due to safety findings or lack of efficacy findings, or is paused until Stage 1 efficacy is observed, non-randomized assignments may proceed within the open dose level expansion cohort. This hypothesis will require a dose cohort total of 16 for a Phase 2 Dose Expansion study total of 32 subjects.

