### 9.5.2. Analysis of Simon 2-stage Design

The Phase 2 Dose Expansion portion of the study will consist of 2 dose cohorts. Subjects will be assigned randomly to each Phase 2 cohort, evaluating a dose or schedule chosen by the SRC based on their evaluation of safety data and any PK, pharmacodynamics, and efficacy data obtained during the Phase 1 Dose Escalation portion of the study. Approximately 32 evaluable subjects are anticipated to enroll in Phase 2, with up to 16 subjects randomly assigned each of the 2 dose cohorts. There will be 9 subjects assigned in the first stage of the Simon 2-stage design, with the remaining 7 subjects also being assigned within a dose cohort to complete the second stage of the Phase 2 Dose Expansion portion of the study.

After evaluating the first 9 subjects for efficacy (defined as a reduction in PSA levels of  $\geq 50\%$ ) in Stage 1 (including subjects who received the same dose during Phase 1 of the study), the study will be terminated if  $\leq 1$  subject responds. If the study progresses to Stage 2, an additional 7 subjects will be treated, for a total of up to 16 evaluable subjects per dose cohort. If at least 5 subjects respond out of the total 16 within a dose cohort, there will be demonstration of efficacy of ONCT-534 within the population for this dose cohort and the corresponding null hypothesis will be rejected. Additional subjects may be enrolled to account for unevaluable subjects.

Randomized dose assignment will proceed when both cohorts are open for enrollment. If one of the dose levels is closed due to safety findings or lack of efficacy, or is paused until Stage 1 efficacy is observed, non-randomized assignments may proceed within the open dose level expansion cohort.

The expected maximum sample size in Phase 2 is 32.

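### Phase 2 evaluability and replacement turn on a disease assessment rather than on PSA, so subjects with PSA data for the Simon endpoint can be classed unevaluable and replaced

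*Combined protocol and SAP*

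**What the plan says.** **Endpoint and rule.** Section 9.1.2 tests each dose level "using a Simon 2-stage minimax design to exclude a response rate of < 10" per cent, with a hypothesized rate of at least 40%, "using a one-sided type I error rate of 0.025 with 80% power". Response is a PSA reduction of at least 50%. Nine subjects enter Stage 1, the dose continues with at least 2 responses, and the null is rejected with at least 5 responses in 16. Section 9.5.2 confirms that the efficacy measure is PSA ("After evaluating the first 9 subjects for efficacy (defined as a reduction in PSA levels of" at least 50%), counts same-dose Phase 1 subjects in Stage 1, and describes the 16 as evaluable.

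**Evaluability.** Section 9.2 has one efficacy-evaluable definition. It requires that subjects "complete at least one post-treatment disease assessment" and does not mention PSA.

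**Replacement.** Under Section 7.2 a Phase 2 subject may be replaced, after discussion with the Sponsor, "if they are not evaluable for efficacy (as defined in Section 9.2) for the purpose of estimating clinical activity of ONCT-534" and if he discontinued for reasons not related to study drug or progression. Section 9.5.2 separately allows more subjects to be enrolled to make up for unevaluable ones and states no limit on reason.

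**What a disease assessment is.** The synopsis (Study Procedures) speaks of "disease assessments by computed tomography scan and bone scan" and lists PSA among the blood tests. Section 8.1.1.4 lists "Disease assessment to verify measurable or evaluable disease" with a pointer to Section 8.2, and PSA level as a separate item pointing to Section 8.1.6. Section 8.2 deals with soft-tissue and bone disease and not with PSA.

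**Timing.** Table 1 draws PSA at Weeks 4, 8 and 12 and at the End of Treatment visit. The first on-treatment CT and bone scan are at Week 12, and no scan is marked at End of Treatment. Table 15 calls Week 9 the first on-treatment scan. The two tables need to be reconciled, but both times fall after the Week 4 PSA.

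**The concern.** The variable that decides who is evaluable is not the variable being tested. A subject who withdraws consent or is lost at Week 10 may have PSA values from Weeks 4 and 8, and perhaps from the End of Treatment visit, yet have no scan. On the documents' usage he is not evaluable, and Section 7.2 then allows him to be replaced. The protocol describes no blinding and PSA is read locally (Section 8.1.6), so his values can be known when replacement is discussed.

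The Simon counts assume that subjects are included without regard to outcome. If those replaced tend to be men whose PSA has not fallen, the cohort gets extra draws at the same thresholds, and both the Stage 1 decision and the final efficacy claim become easier to reach.

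**Working it through.** **Inputs.** From Section 9.1.2: null rate 0.10, alternative 0.40, n1 = 9, N = 16, continue if at least 2, reject if at least 5, one-sided 0.025, power 80%. The documents give no dropout rate, so every loss pattern below is an assumption.

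**Step 1: reproduce the plan's design.** With true rate p,

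P(reject) = Σ over x = 2..9 of Bin(x; 9, p) × P(Bin(7, p) ≥ 5 − x).

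At p = 0.10:

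| Stage 1 responses | Probability | Chance of reaching 5 | Product |
|---|---|---|---|
| 2 | 0.1722 | 0.0257 | 0.0044 |
| 3 | 0.0446 | 0.1497 | 0.0067 |
| 4 | 0.0074 | 0.5217 | 0.0039 |
| 5 or more | 0.0009 | 1 | 0.0009 |

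The sum is 0.0159. At p = 0.40 the same formula gives 0.815. Both meet the stated limits, and an exhaustive search returns 9/16 as a minimax design. The slack in type I error is 0.025 − 0.0159 = 0.0091.

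**Step 2: loss unrelated to PSA.** If a share d leaves regardless of response, the rate among those kept is p(1 − d)/(1 − d) = p. Type I error stays at 0.0159.

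**Step 3: replacing PSA non-responders.** Replacing k1 non-responders in Stage 1 and k2 in Stage 2 amounts to 9 + k1 and then 7 + k2 draws with unchanged thresholds. At p = 0.10, per cohort:

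| Replaced (Stage 1, Stage 2) | Type I error |
|---|---|
| none | 0.0159 |
| one (0,1) or (1,0) | 0.0200 or 0.0210 |
| two (0,2), (1,1) or (2,0) | 0.0246, 0.0261 or 0.0271 |
| four (2,2) | 0.0397 |

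**Step 4: selective loss as a rate.** Suppose only PSA non-responders leave before the scan, and all are replaced. If d is a share of treated subjects, the rate among evaluable subjects is 0.10/(1 − d). If d is a share of non-responders, it is 0.10/(0.10 + 0.90(1 − d)).

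| d | Type I error, d of treated | Type I error, d of non-responders |
|---|---|---|
| 10% | 0.0242 | 0.0231 |
| 20% | 0.0381 | 0.0347 |
| 30% | 0.0624 | 0.0536 |

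Type I error passes 0.025 when the rate among evaluable subjects is about 11.2%. That is d of about 12.0% of non-responders, or 0.9 × 12.0% = 10.8% of treated subjects.

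**The case against.** Several points on the other side are sound.

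- Section 9.2 never says scan. A reader might infer that it requires one outright, but that reading comes from how the synopsis and Sections 8.1.1.4 and 8.2 use the term. Section 8.2 also admits clinical examination for extra-skeletal disease, and targeted examinations occur before Week 12. What is established is that the definition omits PSA and uses a term that elsewhere stands apart from PSA.
- A reader might infer that any subject doing badly can be swapped out. Section 7.2 does not support this: it bars replacement after drug-related or progression-related discontinuation, and progression is the obvious route from non-response to leaving. Withdrawal of consent and loss to follow-up remain, as does the sentence in Section 9.5.2 that carries no such bar.
- A reader might treat flat Week 4 and Week 8 values as a settled failure. Section 9.5.3 defines PSA50 by earliest attainment with no fixed timepoint, so such a subject has an incomplete outcome. Only an early responder's outcome is settled, and replacing him would work against the drug.
- It is not stated that an early PSA responder without a scan drops from the numerator. Section 9.5.3 names no population for PSA50.
- Nothing in the documents links PSA non-response to consent withdrawal or loss. A single replacement leaves type I error below 0.025, and so does the 10% selective-loss case.

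These points limit the size of the problem. They do not remove the mismatch between the endpoint and the definition of who counts for it.

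**Conclusion.** The mismatch stands: the Simon endpoint is PSA50, but evaluability and replacement are tied to a disease assessment. As written, Sections 7.2, 9.2 and 9.5.2 allow a subject with post-treatment PSA values to be set aside and replaced.

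It would go too far to conclude that the test exceeds its stated 2.5% or that the sample size is wrong. The design reproduces, and type I error is unaffected if loss is unrelated to PSA. Breaching 0.025 takes about two replaced PSA non-responders in a cohort, or selective loss of about 11–12%; at 20% it is 0.035–0.038. These figures assume that responders never leave early and that every leaver is replaced by a route the protocol permits, so they show a range and not a forecast. The point deserves correction because the rule decides whether each dose passes Stage 1 and whether efficacy is claimed, and because the correction is cheap.

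**What to change.** - **Section 9.2:** add a PSA-evaluable set for the Simon test. It should hold all subjects counted at that dose, including the same-dose Phase 1 subjects that Section 9.5.2 counts in Stage 1, who received ONCT-534 and have a baseline PSA and at least one post-treatment PSA, with or without a scan. Those who have not reached a 50% decline by their last available PSA count as non-responders.
- **Sections 7.2 and 9.5.2:** state that no one in this set may be replaced or made up for in the Simon test. Only subjects with no post-treatment PSA may be replaced, subject to the reason limit already in Section 7.2.
- **Section 9.5.3:** name the PSA-evaluable set as the PSA50 denominator. Keep the disease-assessment-based set for radiographic endpoints.
- **Sensitivity analysis:** report all treated subjects, with those lacking a post-treatment PSA counted as non-responders. This is better as a sensitivity analysis than as the main rule. With 16 treated and loss unrelated to response, power would fall to 0.770 at 5% loss (rate 0.40 × 0.95 = 0.38) and 0.718 at 10% (0.40 × 0.90 = 0.36).
- **Tables 1 and 15:** reconcile the time of the first on-treatment scan.

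The cost is wording and one extra analysis, with no added visits or samples. The 9/16 design keeps type I error 0.0159 and power 0.815. The observed PSA50 rate may be slightly lower, because early leavers with PSA values but no 50% decline count as non-responders.
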